
lateral to the outer canthus of the left eye and 1 cm above and lateral to the outer canthus of the right eve. Two surface EMG electrodes will be taped onto the chin 2 cm apart. Additional leads will be used to measure leg movements and breathing in order to rule out the presence of occult sleep disorders. Two electrodes will be taped over the anterior tibialis muscle of each leg to detect leg movements during the night. Flexible Resp-EZ belts will be placed around the abdomen and chest to measure breathingrelated movements during the night. A nasal cannula will be used to detect pressure and an oximeter probe will be placed on the finger to measure blood oxygen saturation. Records will be scored in 30second epochs according to standard criteria. PSG data will be used to compute standard sleep architecture variables of the amount of each stage of sleep in terms of minutes and percentage of total sleep time. In addition the following sleep continuity variables will be computed: sleep latency (SL: time from lights out to the first epoch of stage 2 or higher), total sleep time (TST), wake after sleep onset (WASO; number of minutes spent awake between lights out and lights on), and sleep efficiency (SE; total sleep time divided by the total recording period). Additionally, our technicians will attached two sensors to the chest area of the subjects in order to measure respiration and test the sensors to see the accuracy of detecting sleep apnea. TatchSleep is a flexible, thin, and wireless adhesive patch designed to collect physiological parameters related to sleep disorders in patients. Each patch consists of a wearable sensor and a bottom layer of double coat medical-grade adhesive. This adhesive is safe for patient use and enables the patch to stay affixed to the body throughout the night. The sensor also connects directly to a battery which is hidden within the patch. During the study, patients will be asked to wear three patches. Data from the patches are transmitted wirelessly throughout the night to a companion mobile application, which stores the data for clinicians to upload to a sleep analysis platform. Upon waking, wires will be removed and the subjects will be allowed to shower. Those in the insomnia group who choose to participate in the optional second part of the protocol will have a fasted blood draw at this visit. Study staff will walk the subjects over to CHPS outpatient. Around 8:00 AM a lumbar puncture will be performed by a neurology fellow to collect 25 mL of CSF. Prior to the lumbar puncture the neurology fellow will conduct a neurological exam including fundoscopic exam, in order to rule out any contraindications to the procedure such as a coagulopathy or central mass lesion. If contraindications are found, the lumbar puncture will not be performed and the subject will be withdrawn from all further study procedures. If no contraindications are found, a small, specialized needle called a sprotte needle will introduced through an introducer. This type of needle has been demonstrated to reduce risk of headache. 25 mL of CSF will be collected and stored in polypropylene transfer tubes. In addition, bedrest for one or more hours immediately after the procedure will be recommended to the participant. Oral hydration will be encouraged to help reduce risk of headache. After final samples are taken participants will have completed the protocol and will be free to leave. CSF Analysis: Analysis 1: Endogenous ABO levels in human CSF will be measured in a blind fashion in a flow-based ABO-specific sandwich ELISA using the Erenna immunoassay system (Millipore, Temecula, CA), described in Savage et al 2014 JN. In brief, Mercks proprietary 19.3 antibody coupled to paramagnetic microparticles will be used to capture ABO, repeatedly washed with assay-specific proprietary buffers, and detected using a fluor-labeled detection antibody, 82E1 (IBL, Minneapolis, MN). Human CSF samples (100 uL/well) will be loaded in a blinded fashion in triplicate. The standards (ADDL), prepared in-house, will be run alongside CSF samples in triplicate using a 12-point ¹/₂ serial dilution between 42 pg/mL and 0.04 pg/mL. Statistical analysis of the data, including limit of detection (LOD) for the assay (defined as 2 x SD Bkg/slope with percent coefficient of variance 20%) and unknown ABO concentrations will be calculated using Singulex Sgx link and GraphPad Prism (GraphPad Software, Inc., San Diego, CA) software. Analysis 2: OxA concentrations in CSF will be quantified by an in-house ELISA developed using Meso Scale Discovery (MSD) electrochemiluminescence detection technology platform (Gaithersburg, MD, USA). Purified polyclonal IgG (G-003-36, Phoenix Peptide, Burlingame, CA, USA), raised in rabbit against OxA (amino acids 16-33), will be used as a capture antibody. Goat anti-human polyclonal antibody against OxA (N-18) (sc-26491, Santa Cruz Biotechnology Inc., Santa Cruz, CA, USA) will be used as a primary detection antibody. Sulfo-Tag labeled anti-goat antibody, raised in donkey, will be used as a secondary detection antibody and will be provided by MSD (R32AG-5). Blinded CSF samples will be run in triplicate alongside OxA standard (run as a 10-point 1/3 serial dilution between 30,000 and 4.57 pg/mL). Statistical analysis of the data, including lowest detection limit (LDL) for the assay (defined as 2 x SD Bkg/slope with percent coefficient of variance 20%) and unknown OxA concentrations will be calculated by extrapolating a nonlinear regression curve (sigmoidal, 4PL, X is log (Concentration)) and will be corrected for weight by 1/Y² using GraphPad Prism (GraphPad Software, Inc., San Diego, CA) software.

The following documents are currently attached to this item:

There are no documents attached for this item.

Deception

Does your project use deception? Deception could be considered any direct misinformation presented to the subject or omission of key information pertaining to the design or nature of the project. No

International Research

Are you conducting research outside of the United States? No

Analysis Plan

Paired-samples t-tests will be conducted to compare each of the CSF analytes between patients with chronic insomnia and matched good sleepers. Multiple regression analyses will be used to examine whether CSF orexin levels mediate the relationship between chronic insomnia and AB markers. Mediation analyses will be conducted using a series of linear regression models in which group (insomnia or control) and orexin levels will be treated as independent variables and AB markers will be treated as the dependent variables.

The following documents are currently attached to this item:

There are no documents attached for this item.

Data confidentiality

- x Paper-based records will be kept in a secure location and only be accessible to personnel involved in the study.
- x Computer-based files will only be made available to personnel involved in the study through the use of access privileges and passwords.
- x Prior to access to any study-related information, personnel will be required to sign statements agreeing to protect the security and confidentiality of identifiable information.
- x Wherever feasible, identifiers will be removed from study-related information.

A Certificate of Confidentiality will be obtained, because the research could place the subject at risk of criminal or civil liability or cause damage to the subject's financial standing, employability, or liability.

A waiver of documentation of consent is being requested, because the only link between the subject and the study would be the consent document and the primary risk is a breach of confidentiality. (This is not an option for FDA-regulated research.)

Precautions are in place to ensure the data is secure by using passwords and encryption, because the research involves web-based surveys.

Audio and/or video recordings will be transcribed and then destroyed to eliminate audible identification of subjects.

Subject Confidentiality

Each participant will be assigned a study ID #. All study-related paperwork and computer files will only utilize the ID #. All study files will be stored behind a double lock system at [name]. Only study staff will be able to access the data. All study records will be maintained in locked file cabinets for paper records and electronic files will be stored on an institutionally secured & managed network drive. The master file linking subjects with their ID #s will be kept in a separate locked file cabinet. Following completion of the study and all manuscripts are written, paper records will be removed from electronic files at that point as well.

Sensitive Research Information*

Does this research involve collection of sensitive information about the subjects that should be excluded from the electronic medical record? [NOTE: This does not apply to: 1) research information that would not normally be included in the electronic medical record or 2) information that is in the electronic medical record as part of clinical care.]

Subject Privacy

Privacy refers to the person's desire to control access of others to themselves. Privacy concerns people, whereas confidentiality concerns data. Describe the strategies to protect privacy giving consideration to the following: The degree to which privacy can be expected in the proposed research and the safeguards that will be put into place to respect those boundaries. The methods used to identify and contact potential participants. The settings in which an individual will be interacting with an investigator. The privacy guidelines developed by relevant professions, professional associations and scholarly disciplines (e.g., psychiatry, genetic counseling, oral history, anthropology, psychology).

Participants records will only utilize a study ID # in order to avoid violation of privacy. Names of participants will not be shared outside of the study staff, except to the extent required by law. Participants will be asked to indicate their preferred means of contact (phone, email, etc). All study visits will take place in a private room and the door will be closed to maintain privacy.

Disclosures

Will any data or specimens from Penn participants OR other research generated work product (e.g., intellectual property) be disclosed to any individuals, entities, or vendors, etc. outside of Penn? No

Data Protection*

x Name
\mathbf{x} Street address, city, county, precinct, zip code, and equivalent geocodes
x All elements of dates (except year) for dates directly related to an individual and all ages over 89
x Telephone and fax number
x Electronic mail addresses
x Social security numbers
x Medical record numbers
Health plan ID numbers
Account numbers
Certificate/license numbers
Vehicle identifiers and serial numbers, including license plate numbers
Device identifiers/serial numbers
Web addresses (URLs)
Internet IP addresses
Biometric identifiers, incl. finger and voice prints
Full face photographic images and any comparable images
Any other unique identifying number, characteristic, or code
None

Does your research request both a waiver of HIPAA authorization for collection of patient information and involve providing Protected Health Information ("PHI") that is classified as a "limited data set" (city/town/state/zip code, dates except year, ages less than 90 or aggregate report for over 90) to a recipient outside of the University of Pennsylvania covered entity? No

Tissue Specimens Obtained as Part of Research*

Are Tissue Specimens being obtained for research? Yes

No

Tissue Specimens - Collected during regular care*

Will tissue specimens be collected during regulator clinical care (for treatment or diagnosis)? No

Tissue Specimens - otherwise discarded*

Would specimens otherwise be discarded? No

Tissue Specimens - publicly available*

Will tissue specimens be publicly available? No

Tissue Specimens - Collected as part of research protocol*

Will tissue specimens be collected as part of the research protocol? Yes

Tissue Specimens - Banking of blood, tissue etc. for future use*

Does research involve banking of blood, tissue, etc. for future use? Yes

Genetic testing

If genetic testing is involved, describe the nature of the tests, including if the testing is predicative or exploratory in nature. If predictive, please describe plan for disclosing results to subjects and provision of genetic counseling. Describe how subject confidentiality will be protected Note: If no genetic testing is to be obtained, write: "Not applicable."

Not Applicable

Consent

1. Consent Process

Overview

Study personnel will meet with each individual virtually and describe the study in detail. Individuals will be provided with the combined consent / HIPAA form to read. They will have the opportunity to ask questions and discuss participation with other family members. Individuals will be asked to sign a consent form on RedCAP. Individuals who continue participation will provide written informed consent will be given a copy of the consent form for their records at their overnight sleep study.

Children and Adolescents

Not Applicable.

Adult Subjects Not Competent to Give Consent Not Applicable.

2. Waiver of Consent

Waiver or Alteration of Informed Consent* No Waiver Requested

Minimal Risk*

Impact on Subject Rights and Welfare*

Waiver Essential to Research*

Additional Information to Subjects

Written Statement of Research* No

The following documents are currently attached to this item:

There are no documents attached for this item.

Risk / Benefit

Potential Study Risks

There is no substantial risk associated with the completion of the initial evaluation, though the subject will be asked to respond honestly to personal questions. Risks associated with polysomnography: There are few risks associated with the sleep study procedure. However, some people do experience minor discomfort (dry skin, rash) from having the skin cleansed and sensors placed on the skin over the course of the in laboratory studies. Risk of Lumbar Puncture: There is the risk of brain swelling or herniation if the subject has particular neurological abnormalities (e.g. papilledema, mass lesion, Chiari malformation). The neurology fellow performing the LP will conduct a neurological exam with fundoscopic exam to rule out these contraindications and will only proceed if there is no evidence of these risks. The lumbar puncture may cause pain at the site where the needle goes in and the spinal fluid is taken. There is a small risk of infection or bleeding. After the lumbar puncture, there is a risk of headache. To minimize the risk of a headache, the doctor will use a small, specialized needle, a sprotte needle introduced through an introducer. This type of needle has been demonstrated to reduce risk of headache. In addition, bedrest for one or more hours immediately after the procedure will be recommended to the participant. Finally, oral hydration will be encouraged to help reduce risk of headache. If headache does occur, it is usually mild and can be controlled with bedrest, hydration (with oral fluids), and acetaminophen or NSAIDS. Rarely, the headache is severe and may require additional treatment with a blood patch. In this procedure, a small amount of the patient's own blood is injected into the lumbar puncture site. This procedure is generally effective in stopping the headache. Although very rare, it is possible to have an allergic reaction to the local anesthetic used for the lumbar puncture. Signs of an allergic reaction include swelling and/or a rash on the skin where the anesthetic was injected. The patient will be asked about prior allergies to lidocaine and will be monitored for evidence of this reaction. There is a small risk of hemorrhage related to lumbar puncture. This risk will be minimized by checking a platelet count and coagulation studies (PT/PTT) prior to the lumbar puncture. To further minimize any possible risk, the lumbar puncture will be done by a neurology resident who is specifically trained in the procedure. Potential sources of research risk of this proposed investigation include the burden to participants cause by the amount of time asked of them, performance of the actigraphy and sleep study, and the confidentiality of data obtained. We do not consider the time demands on participants a serious risk and they can withdraw at any time. In addition, study staff will be trained to minimizr the burden on research involving human participants, breach of confidentiality of personal data obtained as part of this study is a potential risk to participants.

Potential Study Benefits

It is possible that the sleep study could identify sleep disorders that participants are unaware of, enabling them to seek treatment. There are no other benefits to the individual for participation. The knowledge we expect to gain from this study will be used to better understand the relationship between chronic insomnia and dementia.

Alternatives to Participation (optional)

The subject can choose to not participate.

Data and Safety Monitoring

Principal Investigator

The following documents are currently attached to this item:

There are no documents attached for this item.

Risk / Benefit Assessment

The procedures in this study are greater than ordinarily encountered in daily life, but they are commonly used without problems in the context of biomedical research. As such this study is moderate

General Attachments

The following documents are currently attached to this item:

There are no documents attached for this item.

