The longstanding view has been that insomnia, and other forms of sleep disturbance, emerge as a consequence of dementia and are the result of progressive neuronal damage. However, there is growing evidence that the direction of causation may go both ways, with sleep disturbance potentially increasing vulnerability to dementia. Longitudinal studies have found that sleep disturbance often precedes and increases risk for dementia by several years. The purpose of this study is to examine the relationship

between chronic insomnia and dementia biomarkers and orexin levels found in cerebrospinal fluid (CSF). Fifteen adults age 30-50 with chronic insomnia and age- and gender-matched good sleepers will undergo overnight polysomnography and CSF sampling in the morning.

Objectives

Overall objectives

Patients with dementia very frequently have disturbed sleep that is thought to be caused, in part, by the dementing illness. There is growing evidence of the reverse direction of causation, with sleep disturbance increasing vulnerability to dementia. The recently-discovered glymphatic system, by which waste from neural metabolism is cleared from the brain, may be a mechanism for the sleep-dementia link. The goal of this project is to examine the relationship between chronic sleep disturbance (insomnia) and dementia biomarkers and orexin levels as assessed in cerebrospinal fluid (CSF). Fifteen adults age 30-50 with chronic insomnia and age- and gender-matched good sleepers will undergo overnight polysomnography and morning CSF sampling. These data will be used to address the following specific aims: Specific Aim 1: To examine the association between chronic insomnia and CSF markers of dementia. Hypothesis 1: Chronic insomnia will be associated with higher levels of CSF AB markers compared to good sleepers. Specific Aim 2 (exploratory): To examine the role of orexin in mediating the relationship between chronic insomnia and CSF markers of dementia. Hypothesis 2: Higher CSF orexin levels will mediate the relationship between chronic insomnia and A markers.

Primary outcome variable(s)

Dementia biomarkers in cerebrospinal fluid

Secondary outcome variable(s)

CSF orexin levels

Background

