Patients with Alzheimers dementia frequently experience sleep disturbance that gradual worsens with increasing severity of the disorder. For caregivers, having a patient with dementia awake during the night is one of the primary reasons cited for nursing home placement. The longstanding view has been that insomnia, and other forms of sleep disturbance, emerge as a consequence of dementia and are the result of progressive neuronal damage. For example, Alzheimers dementia has been shown to target the suprachiasmatic nucleus, the master clock of the body. There is growing evidence that the direction of causation may go both ways, with sleep disturbance potentially increasing vulnerability to dementia. Longitudinal studies have found that sleep disturbance often precedes and increases risk for dementia by several years. In older adults without cognitive impairment, self-reported insomnia has been found to be associated with greater beta amyloid burden as assessed with PET imaging. One mechanism that could explain this relationship is the recently-discovered glymphatic system, through which potentially toxic byproducts of neural metabolism, such as A, are cleared from the nervous system. Metabolic solutes are excreted into the interstitial fluid, which then flow through interstitial space and pass into cerebrospinal fluid (CSF) for clearance. During sleep, the interstitial space increases by 60%, allowing greater transport of metabolites. Acute sleep deprivation in mice leads to an increase in A levels in CSF. These studies demonstrate that disturbed sleep increases markers of Alzheimers disease and may increase vulnerability to the disorder. While the mechanisms underlying the glymphatic system are still under investigation, there is increasing evidence that the peptide orexin plays a crucial role. In humans, high CSF concentration of orexin-A was associated with increased phosphorylated tau. In an animal model of Alzheimers disease, genetic deletion of orexin led to only moderate increases in sleep duration but strongly suppressed the formation of amyloid plaques. In a second study of this mouse model, delivery of an orexin antagonist significantly inhibited amyloid plaque formation. There is a need to better understand the role that orexin plays in the link between insomnia and Alzheimers disease. Much of the literature in this area utilizes models of acute sleep disturbance, usually total sleep deprivation. Less is known about the impact of chronic sleep disturbance as it occurs in the general population, most notably in the form of chronic insomnia. Given that AB levels accumulate for up to years prior to the onset of dementia, improved understanding of the mechanisms through which deposition occurs could dramatically shift the landscape from treatment of dementia to one of prevention in two ways. First, promotion of good sleep throughout the lifespan may decrease vulnerability to dementia. Second, sleep research may provide a window into the physiology of the glymphatic system and lead to novel insights for non-sleep approaches for prevention and treatment. Given the commercial availability of an FDAapproved orexin antagonist, there may be tremendous opportunity to decrease risk for dementia through

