
the treatment of chronic insomnia.

Study Design

Phase* Not applicable

Design

Laboratory Observational study

Study duration

The total duration of the study will be 24 months, each participants duration in the study will be approximately 4 weeks.

Resources necessary for human research protection

Describe research staff and justify that the staff are adequate in number and qualifications to conduct the research. Describe how you will ensure that all staff assisting with the research are adequately informed about the protocol and their research related duties. Please allow adequate time for the researchers to conduct and complete the research. Please confirm that there are adequate facilities for the research.

The principal investigator involved in this project has extensive experience in sleep research, including having a history of success in conducting studies with CSF sampling. A study coordinator will be hired for this study and they will be trained in all designated duties and responsibilities of the study. [name] will provide oversight of the study coordinator. The study will be conducted at the CTRC, where there are sufficient facilities and resources available.

Characteristics of the Study Population

Target population

Fifteen adults age 30-60 with chronic insomnia and fifteen age- and gender-matched good sleepers.

Subjects enrolled by Penn Researchers 30

Subjects enrolled by Collaborating Researchers

0

Accrual

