Participants will be recruited through targeted advertisements in the Philadelphia area community. We have a track record of success in recruitment through these approaches. To estimate the appropriate sample sizes, statistical calculations were carried out using pilot data obtained from OxA and ABO measurements from N=6 individuals. Specifically, two-sided two-sample t-test was utilized for a two-group parallel design study which compared chronic insomniacs with good sleepers. For OxA, sample sizes needed to detect intended effect sizes (differences of 30%, 40%, and 50) were estimated at 80% power. For ABO, sample sizes were calculated to significantly detect the differences between two groups of 50%, 100%, and 150% at 80% power. Power calculations were performed on OxA and ABO in raw and natural log scales, respectively, after examining the normality of data with residual plots. Variability estimates at each time point were obtained as averages of sample standard deviations of two treatment groups per time point. As such, N=15/group would be sufficient to identify changes in the 8 AM samples considering effect sizes equal or greater than 30% and 100% for OxA and ABO, respectively.

Key inclusion criteria

All subjects must meet the following criteria: -Age 30-60 -Men and women To be included in the insomnia group, subjects must meet the following DSM5 Diagnostic Criteria for insomnia disorder: - dissatisfaction with sleep quantity or quality (difficulty initiating or maintaining sleep, or waking up too early) despite adequate opportunity for sleep -sleep disturbance causes clinical significant distress or impairment in functioning -present at least 3 times per week for at least 3 months -sleep disturbance is

not better explained by a medical or psychiatric condition or based on the effects of a substance - Insomnia Severity Index (ISI) score 14 or greater.

Key exclusion criteria

-Diagnosis or evidence of sleep disorders other than insomnia as determined by the screening questionnaires and clinical history -Women who have been pregnant or lactating within the past six months -Non-fluency in spoken or written English -Current or past month shiftwork defined as working during the evening or night shift -Current use of medications or OTC products that impact sleep - Evidence of neurological abnormalities that could include the risks associated with lumbar puncture (e.g.papilledema, mass lesion, Chiari malformation).

Vulnerable Populations

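### The Aim 2 regressions give the same result whether CSF orexin is a mediator or a common cause, so mediation cannot be concluded from this design

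*Combined protocol and SAP*

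**What the plan says.** Overall objectives labels the aim exploratory, "Specific Aim 2 (exploratory): To examine the role of orexin in mediating the relationship between chronic insomnia and CSF markers of dementia", and follows it with the hypothesis "Higher CSF orexin levels will mediate the relationship between chronic insomnia and A markers" (the A markers are the AB markers; a character was lost in the text). CSF orexin is the secondary outcome. The Analysis Plan states: "Multiple regression analyses will be used to examine whether CSF orexin levels mediate the relationship between chronic insomnia and AB markers". It describes a series of linear models with group and orexin as independent variables and AB markers as dependent variables.

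The design is given as "Laboratory Observational study". Among the inclusion criteria for the insomnia group is a complaint "present at least 3 times per week for at least 3 months". On sampling, Procedures says: "Around 8:00 AM a lumbar puncture will be performed by a neurology fellow to collect 25 mL of CSF". Both the AB (ABO) and the orexin-A assays use CSF from that collection. Study duration adds that "each participants duration in the study will be approximately 4 weeks", and no second CSF sample is described. The Background reports that in a mouse model "genetic deletion of orexin led to only moderate increases in sleep duration but strongly suppressed the formation of amyloid plaques".

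**The concern.** Mediation is a statement about order: insomnia changes orexin, and orexin then changes AB. The plan tests it with coefficients that carry no information about order. If orexin was already high before the insomnia began, and contributes both to the insomnia and to AB, orexin is a confounder of the insomnia-AB association. Adding it to the model then removes bias. Under mediation, adding it removes part of a real effect. The printed output is the same.

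The meaning of the result is at stake. Under mediation, the attenuated portion is an effect of insomnia. Under a common cause, that same portion is not an effect of insomnia at all, and improving sleep without changing orexin would not remove it. This bears on the Background's remark that promoting good sleep across the lifespan may reduce vulnerability to dementia. The available text states no causal-order assumption, sensitivity analysis or limit on interpretation for Aim 2.

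**Working it through.** **The plan's own figure.** There is none for Aim 2. The 15 per group in Accrual is for two-group comparisons at 80% power. It cannot be reproduced, because the pilot SDs and alpha are not given. With two-sided alpha of 0.05 (assumed), 15 per group detects a standardised difference of 1.06. That value is used below only as a convenient orexin difference.

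**Why the two structures coincide.** Let X be group, M orexin and Y the AB marker.

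- Mediator: the joint distribution is f(x) · f(m | x) · f(y | m, x).
- Common cause: it is f(m) · f(x | m) · f(y | m, x).

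By Bayes' rule f(x) · f(m | x) = f(m) · f(x | m), so every mediator model has a common-cause model with the same joint distribution. For example, if orexin is normal with unit SD and means 0 and δ in two equal groups, the matching model is logit P(X = 1 | M) = δM − δ²/2. Selecting participants by group does not help, since the distribution of (M, Y) given X is the same in both.

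**What the regressions estimate.** Let a be the coefficient of M on X, c that of Y on X alone, and c′ and b those of Y on X and M together. In least squares c = c′ + a·b in any data set, whichever way the arrows point.

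**Numbers.** Assumed, not from the documents: a = 1.06, b = 0.5, c′ = 0.3 or 0, unit residual SDs. By hand, a·b = 1.06 × 0.5 = 0.53. With c′ = 0.3, c = 0.3 + 0.53 = 0.83 and the proportion attributed to orexin is 0.53/0.83 = 0.64. Simulation with 1,000,000 people per structure gave:

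| Structure | c′ set to | a | b | c | c′ | a·b | a·b / c |
|---|---|---|---|---|---|---|---|
| Mediator | 0.3 | 1.060 | 0.501 | 0.832 | 0.301 | 0.532 | 0.64 |
| Common cause | 0.3 | 1.057 | 0.500 | 0.829 | 0.301 | 0.528 | 0.64 |
| Mediator | 0 | 1.063 | 0.501 | 0.532 | 0.000 | 0.532 | 1.00 |
| Common cause | 0 | 1.058 | 0.501 | 0.529 | −0.001 | 0.530 | 1.00 |

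With 15 per group (4,000 replicates, c′ = 0.3), mean a·b was 0.537 (SD 0.291) under mediation and 0.528 (SD 0.280) under a common cause. Both paths were significant in 55.8% and 55.7% of replicates.

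**What differs is the truth behind the numbers.** With c′ = 0.3, the effect of insomnia on AB is 0.83 under mediation and 0.30 under a common cause; the other 0.53 is confounding. With c′ = 0 it is 0.53 under mediation and zero under a common cause.

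**Does the protocol supply the missing order?** Three parts bear on it:

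- Key inclusion criteria and Procedures: insomnia is established by at least 3 months of history, and a week of actigraphy precedes the laboratory night. Insomnia thus precedes the CSF sample, but orexin before onset remains unseen.
- Procedures: orexin and AB come from the same collection, so neither is measured ahead of the other. An optional second part is mentioned for the insomnia group, but the Analysis Plan uses no data from it.
- Background: removing orexin changed both sleep and plaque formation in mice. This fits orexin upstream of both. It also supports the orexin-to-amyloid step that mediation needs.

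**The case against.** The strongest reply is that Aim 2 is labelled exploratory, orexin is a secondary outcome, and the Analysis Plan says only that mediation will be examined. Cross-sectional mediation analyses share this limitation, and it can be handled when results are interpreted. No sample, measurement or model would change. That stands as a reason to treat this as a wording matter. It does not remove the point: an exploratory label lowers the weight of a finding without telling the reader that causal order was assumed, and Hypothesis 2 is a directional statement with no caveat.

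A reader might also infer more than the documents support:

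- That the plan will declare mediation. The Analysis Plan has no decision rule, joint test or reporting commitment for Aim 2. The requirement that both paths be significant is a device of the illustration.
- That exposure, mediator and outcome are all captured at one moment. This is true of orexin and AB only.
- That the Background shows orexin to be the common cause. It makes that reading plausible, and it does not exclude insomnia raising orexin.
- That the orexin-antagonist rationale fails. If orexin is a common cause, acting on orexin remains relevant.
- That a figure near 56% is an error rate for this study. Another set of assumed inputs (about a 1 SD orexin difference, slope 0.7) gave 68.9% and 68.5%. The level follows the inputs; only the match between structures is informative, and it is expected by construction.

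**Conclusion.** The point holds in a limited form. The planned regressions can show whether the insomnia-AB association is attenuated after accounting for orexin. They cannot show that orexin mediates it, and more participants would not change that. The size is best stated as what is left undetermined: the whole attenuated portion, a·b, may be an indirect effect of insomnia or may be confounding.

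This rests on insomnia not being assigned, on orexin before onset being unobserved, on a single CSF collection, and on no causal-order assumption being stated. It does not depend on the simulated effect sizes. Aim 1, which is worded as an association, is unaffected. The change is worth making because it alters what the study may conclude, but it concerns an exploratory aim and leaves the analysis intact.

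**What to change.** Keep the regressions and the exploratory label. Change the wording in two places.

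- Overall objectives. Aim 2 (exploratory): *to examine whether the association between chronic insomnia and CSF AB markers is attenuated after accounting for CSF orexin.* Hypothesis 2: *the difference in AB markers between the insomnia and good-sleeper groups will be smaller after accounting for CSF orexin.*
- Analysis Plan. Replace the language of mediation to match, and add: *The causal order of insomnia, orexin and AB is assumed and not tested. Attenuation is compatible with orexin as a mediator or as a common cause of insomnia and AB. Mediation will not be concluded from this single-sample design.*

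Participants, procedures, assays, sample size and models stay as they are. The cost is two short edits and a weaker claim for an exploratory aim.
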